8.6. Physical Examinations

Physical examinations will be performed at the time points detailed in Table 4 and Table 5 of the study protocol. Physical examinations will not be summarized. Any finding will be listed.

Weight, height and BMI will be assessed as a part of the vital signs (Section 8.8).

8.7. Neurological Examinations

Neurological examinations will be performed at the time points detailed in Table 4 and Table 5 of the study protocol. Neurological examinations will not be summarized. Any finding will be listed.

8.8. Vital Signs

Vital signs (blood pressure [BP; systolic/diastolic], respiratory rate, body temperature, and pulse) will be measured at the time points detailed in [Table 2](#) and [Table 3](#).

Vital signs values and changes from baseline to each visit will be summarized using descriptive statistics.

Orthostatic systolic and diastolic BP and pulse will be calculated as supine or semi erect/seated measurement minus standing measurement and values and changes from baseline to each visit will be summarized using descriptive statistics.

Orthostatic hypotension (determined by BP measurements only; positive value in case of abnormality) is defined as having either a ≥ 20 mmHg reduction from supine to standing position in systolic blood pressure (SBP) or ≥ 10 mmHg reduction from supine to standing position in diastolic blood pressure (DBP) or both. Orthostatic tachycardia is defined as pulse increase ≥ 20 bpm from supine to standing position.

Summaries of potentially clinically significant abnormal values will include all post-baseline values (including scheduled, unscheduled, and withdrawal visits). The incidence of potentially clinically significant abnormal values will be summarized using descriptive statistics with the criteria specified in [Table 8](#).

[Table 8](#) specifies the criteria for identifying vital signs as potentially clinically significant abnormal values.

Table 8: Criteria for Potentially Clinically Significant Vital Signs

Vital Sign (unit)	Age	Potentially Clinically Significant Low Criterion value	Potentially Clinically Significant High Criterion value
SBP (supine) (mmHg)	6-12	Value ≤ 70 and ≥ 20 decrease from baseline	Value ≥ 120 and ≥ 20 increase from baseline
	13-18	Value ≤ 90 and ≥ 20 decrease from baseline	Value ≥ 135 and ≥ 20 increase from baseline
DBP (supine) (mmHg)	6-12	Value ≤ 40 and ≥ 15 decrease from baseline	Value ≥ 80 and ≥ 15 increase from baseline
	13-18	Value ≤ 50 and ≥ 15 decrease from baseline	Value ≥ 90 and ≥ 15 increase from baseline
Pulse rate (supine) (bpm)	6-10	Value ≤ 60 and ≥ 15 decrease from baseline	Value ≥ 135 and ≥ 15 increase from baseline
	11-18	Value ≤ 50 and ≥ 15 decrease from baseline	Value ≥ 120 and ≥ 15 increase from baseline
SBP orthostatic criteria (mmHg)	~	≥ 20 decrease from supine to standing position	NA
DBP orthostatic criteria (mmHg)	~	≥ 10 decrease from supine to standing position	NA
Pulse rate orthostatic criteria (bpm)	~	NA	≥ 20 increase from supine to standing position
Temperature (°C)	~	NA	Value $\geq 38.3^{\circ}\text{C}$ and $\geq 0.8^{\circ}\text{C}$ increase from baseline

The BMI will be computed similarly to description in [Section 5.3](#) at post-baseline visits using weight at visit and last available height measurement.

In addition, normal age and sex-based z-scores and percentiles for BMI will be determined using the WHO growth charts. Age and sex-based BMI categories include: Underweight (< 5 percentile), Normal ($\geq 5 - < 85$ percentile), Overweight ($\geq 85 - < 95$ percentile), Obese (≥ 95 percentile).

Descriptive statistics for weight, height and BMI will be provided. Data will be listed.

For COVID-19 updates, vital Signs are optional at week 3 and week 14, mandatory at Week 7, mandatory at Week 27 and at week 40 if not done at the respective previous visit and mandatory at week 53/ET and week 54. Vital Signs can be measured at home, at a local pharmacy or by the home nursing.

Orthostatic blood pressure and pulse are optional.

8.9. **Electrocardiography**

A 12-lead ECG will be recorded at the time points detailed in Table 4 and Table 5 of the study protocol. All ECGs will be performed after at least 5 minutes rest in a supine or semi-supine position. A qualified physician at a central diagnostic center will be interpreting the ECG. A central ECG Standard 12-lead ECG will record heart rate (HR), PR interval (Time from the beginning of the P wave to the beginning of the QRS complex in electrocardiogram), RR interval (Time between the start of one R wave and the start of the next R wave in the ECG), QT interval, Fridericia's corrected QT interval (QTcF), and QRS duration (Graphical deflections corresponding to ventricular depolarization in a typical electrocardiogram).

All ECG results outside of the reference ranges will be judged by the investigator as belonging to one of the following categories:

- abnormal and not clinically significant
- abnormal and clinically significant

If an abnormal post-baseline QTcF value >500 msec or change from baseline >60 msec is found, the investigator must further evaluate QTcF based on protocol section 7.9.

Shifts (normal and abnormal) from baseline to overall result interpretation and each visit will be summarized using patient counts for the centrally-read interpretation. For overall result interpretation the worst post-baseline finding for the patient (the abnormal finding if there are both normal and abnormal findings) will be used in the summaries. Summary statistics for ECG variables values will be presented. Actual values and changes from baseline to each visit will be summarized using descriptive statistics.

QTcF values will be classified as having QTc prolongation if any of the following conditions are met.

- Confirmed QTcF >450 msec
- Confirmed QTcF >480 msec
- Confirmed QTcF >500 msec
- Increase from baseline QTcF > 60 msec
- Increase from baseline confirmed QTcF > 60 msec

The confirmed QTcF is defined as the average of up to 3 standard ECG values at a visit, or a single summary ECG. If there are more than 3 standard or more than one summary ECG at a visit, then use the last ECGs for the confirmed QTcF.

The number and percentage of patients with QTc prolongation will be summarized overall, and by visit.

The incidence of potentially clinically significant abnormal values for ECG variables will be summarized using descriptive statistics with the criteria presented in [Table 9](#). The summary will be completed by age groups (6 to < 8 years, 8 to < 12 years, 12 to < 16 years, and ≥ 16 years), and overall.

Table 9: Potentially Clinically Significant Values for ECG Variables by Age

ECG parameter (unit) ^a	Age (years old)	Potentially Clinically Significant Low	Potentially Clinically Significant High
Heart Rate (bpm)	6 to <8	< 65	> 115
	8 to <12	< 55	> 110
	12 to <16	< 50	> 105
	≥ 16	< 50	> 100
PR interval (msec)	6 to <8	--	> 160
	8 to <12	--	> 175
	12 to <16	--	> 180
	≥ 16	--	> 200
QRS interval (msec)	6 to <8	--	> 100
	8 to <12	--	> 105
	12 to <16	--	> 110
	≥ 16	--	> 120

^a bpm=beats per minute; HR=heart rate; PR interval =Time from the beginning of the P wave to the beginning of the QRS complex in electrocardiogram; RR interval =Time between the start of one R wave and the start of the next R wave in the ECG; QRS duration =Graphical deflections corresponding to ventricular depolarization in a typical electrocardiogram

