**Analysis of Safety:**

Safety analyses will be presented for the ITT analysis set. Patients that did not receive any TEV-50717 will be excluded from the summaries and presented in listings only.

All adverse events will be coded using the Medical Dictionary for Regulatory Activities (MedDRA). Each patient will be counted only once in each preferred term or system organ class category for the analyses of safety. Summaries will be presented for all adverse events, adverse events determined by the investigator to be related to TEV-50717, serious adverse events, and adverse events causing withdrawal from the study. Patient listings of serious adverse events and adverse events leading to withdrawal will be presented.

Observed values and changes from day 1 in laboratory results and vital signs will be summarized descriptively.

Observed values in ECG parameters will be summarized, and counts and percentages of abnormal findings will be presented. Changes from baseline of the parent study in ECG parameters will be summarized descriptively. In addition, the number and percentage of patients with on-treatment QTcF values  $>450$ ,  $>480$ , or  $>500$  msec and change from day 1  $>30$  or  $>60$  msec will be presented.

The use of concomitant medications will be summarized by therapeutic class using descriptive statistics. Concomitant medications will include all medications taken while the patient is treated with TEV-50717.

Observed values in the children's C-SSRS will be presented for all patients.

Assessments of drug-induced parkinsonism according to the ESRS (subsubscales I and II), of change in behavior according to the CBCL questionnaire, and assessment of sedation according to the ESS questionnaire will be summarized descriptively.

If any patient dies during the study, a listing of deaths will be provided and all relevant information will be discussed in the patient narrative included in the clinical study report.

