### **3.3. Justification for Study Design and Selection of Population**

Currently, there is no approved treatment available for DCP. DCP is a hyperkinetic motor impairment due to a non-progressive disturbance of brain function that occurs in the developing fetal or infant brain, generally before the age of 2 years. DCP has a major debilitating impact on the ability of the child with CP to further develop motor skills. The available treatment options address some of the manifestations of DCP.

The study population will include pediatric and adolescent patients (6 through 18 years of age at the time when they enrolled in the parent study [Study TV50717-CNS-30080]), ie, 6 through 20 years of age when they enroll in TV50717-CNS-30081 study, with DCP with predominant choreiform movement disorder, who have had non-progressive CP symptoms since infancy ( $\leq 2$  years of age), and have completed Study TV50717-CNS-30080. The diagnosis of DCP is based on the Surveillance of Cerebral Palsy in Europe criteria ([Cans 2000](#)). “Predominant” in this instance indicates that the choreiform movement disorder is the main cause of impairment or distress.

Study TV50717-CNS-30081 uses the same versions of scales as in the parent study, to maintain consistency of evaluations between these studies. As such, Study TV50717-CNS-30081 includes some scales that are designated for patients up to 18 years old, although potentially some patients who entered the parent study at age 18 will now be over 18 years old in this extension study.

Consequently, the open-label study design was chosen for this Phase 3 study to determine whether long-term treatment with TEV-50717 results in favorable safety, tolerability, and efficacy findings in children and adolescents with DCP.

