## 4.2. Patient Exclusion Criteria

Patients will not be randomized/enrolled in this study if they meet any of the following criteria:

- a. Patient has clinically significant depression at screening or day 1 of this study.
  - Note: Patients receiving antidepressant therapy may be enrolled if on a stable dose for at least 6 weeks before screening or day 1 (whichever comes first) and anticipated to remain stable (dose and frequency) within the study duration.
- b. Patient has a history of suicidal intent or related behaviors based on medical or psychiatric history or the C-SSRS at screening visit, if performed, or at the day 1 visit, as applicable according to the patient's age:
  - intent to act on suicidal ideation with a specific plan, irrespective of level of ambivalence, at the time of suicidal thought
  - suicidal preparatory acts or behavior
- c. Patient has a history of a previous actual, interrupted, or aborted suicide attempt based on medical or psychiatric history or the C-SSRS at screening visit, if performed, or at the day 1 visit, as applicable according to the patient's age.
- d. Patient has a first-degree relative who has completed suicide.
- e. Patient has received any of the following concomitant medications within the specified exclusionary windows from screening or day 1 (whichever comes first) of this study:
  - within 30 days: tetrabenazine or valbenazine
  - within 21 days: reserpine
  - within 14 days: levodopa, dopamine agonists, and monoamine oxidase inhibitors
- f. Patient has received treatment with stem cells, deep brain stimulation, transmagnetic stimulation, or transcranial direct current stimulation for treatment of abnormal movements or CP since the week 15 visit of Study TV50717-CNS-30080, or the patient is not in a stable clinical condition.
- g. Patient had a surgical procedure since the week 15 visit of Study TV50717-CNS-30080 or is anticipated to have a surgical procedure during the study that, in the opinion of the investigator, makes the patient unsuitable for the study.
- h. Patient has a severe mental disability or an unstable or serious medical illness (eg, epilepsy) that, in the opinion of the investigator, could jeopardize or would compromise the patient's ability to participate in this study.

- i. Patient has a QT interval (QTc) corrected for heart rate using Fridericia's formula (QTcF) value  $>450$  msec on 12-lead ECG at screening or day 1 (whichever comes first) of this study.

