#### 9.6. Safety Endpoints and Analysis

The primary objective of this study is to evaluate the safety and tolerability of long-term therapy with TEV-50717 in children and adolescents with DCP.

The safety measures/endpoints are as follows:

- adverse events
- vital signs
- children's C-SSRS
- ECG parameters
- clinical laboratory parameters (hematology, serum chemistry, and urinalysis)
- ESRS (subscale I and II)
- CBCL
- ESS

Safety analyses will be presented for the ITT analysis set (Section 9.2.1). Patients who did not receive any TEV-50717 will be excluded from the summaries and presented in listings only.

All adverse events will be coded using the Medical Dictionary for Regulatory Activities (MedDRA). Each patient will be counted only once in each preferred term or system organ class (SOC) category for the analyses of safety. Summaries will be presented for all adverse events (overall and by severity), adverse events determined by the investigator to be related to TEV-50717 (ie, reasonable possibility; see Section 7.1.4) (defined as related or with missing relationship) (overall and by severity), serious adverse events, and adverse events causing withdrawal from the study. Patient listings of serious adverse events and adverse events leading to withdrawal will be presented.

Observed values and changes from day 1 in laboratory results and vital signs will be summarized descriptively.

Observed values in ECG parameters will be summarized, and counts and percentages of abnormal findings will be presented. Changes from baseline of the parent study in ECG parameters will be summarized descriptively. In addition, the number and percentage of patients with on-treatment QTcF values >450, >480, or >500 msec and change from day 1 >30 or >60 msec will be presented.

The use of concomitant medications will be summarized by therapeutic class using descriptive statistics. Concomitant medications will include all medications taken while the patient is treated with TEV-50717.

The frequency and severity of suicidal ideation or behavior according to the children's C-SSRS questionnaire will be presented by visit. A shift table for children's C-SSRS categories at day 1, compared to the worst (highest) category during the treatment period, will be presented.

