### 2. Procedures Before TEV-50717 Treatment

#### 2.1 Procedures for Patients Who Enroll Between 1 and <2 Weeks After Study TV50717-CNS-30080 Week 15 Visit

##### a. Data carried over from Study TV50717-CNS-30080 - Screening

- Demographics

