5.3. Demographics and Baseline Characteristics

Patient demographic and baseline characteristics will be summarized using descriptive statistics.

Body mass index (BMI) will be computed as:

$$\text{BMI (kg/m}^2\text{)} = \text{Weight at baseline (kg)}/[\text{Height at screening (m)}^2]$$

Normal age and sex-based z-scores and percentiles for BMI will be determined using the World Health Organization (WHO) growth charts. Age and sex-based BMI categories includes: Underweight (< 5 percentile), Normal ($\geq 5 - < 85$ percentile), Overweight ($\geq 85 - < 95$ percentile), Obese (≥ 95 percentile).

The continuous variables of patient age, weight, height, BMI, BMI WHO adjusted z-scores and percentile, will be summarized using descriptive statistics.

The categorical variables of patient weight group, sex, race, ethnicity, region (United States (US) and non-US), country for non-US, age group (6 to 11 years, 12 to 18 years), CYP2D6 impairment status (Impaired/Not impaired), and BMI categories will be summarized using descriptive statistics for each category. Missing categories will be presented if necessary.

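### SAP 8.9 omits, without declaring it, the patient count for QTcF change above 30 msec that protocol 9.6 promises

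*SAP*

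**What the plan says.** **QTcF.** The protocol makes the promise twice, in the synopsis (Analysis of Safety) and in Section 9.6: "In addition, the number and percentage of patients with on-treatment QTcF values" above 450, 480 or 500 msec, together with "change from day 1 >30 or >60 msec will be presented". SAP 8.9 then fixes what is counted: "QTcF values will be classified as having QTc prolongation if any of the following conditions are met". The conditions are confirmed QTcF above 450, above 480 and above 500, an increase above 60, and a confirmed increase above 60. Confirmed means the average of up to three standard ECGs at a visit, or one summary ECG. Patients meeting these conditions are counted overall and by visit.

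**Precedence and disclosure.** The SAP Introduction says that the SAP governs where the two documents differ, with the differences explained in the clinical study report (CSR). SAP Section 11, the place for changes from the protocol, is marked not applicable. Protocol Section 9 says changes to the analyses will be described in the SAP. Protocol 9.10 also allows deviations to be described in amendments or the CSR.

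**Age.** In the SAP 8.8 table "Criteria for Potentially Clinically Significant Vital Signs" (Table 8), the top supine bands are 13-18 for blood pressure and 11-18 for pulse. Protocol 3.3 expects patients to be "6 through 20 years of age when they enroll in TV50717-CNS-30081 study".

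**Laboratory.** Protocol 9.6 promises summaries of PCS laboratory values on predefined criteria. SAP 8.5 gives descriptive statistics and normal-range shifts, with no PCS cut-offs.

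**The concern.** Safety is the primary objective of this uncontrolled study of about 45 patients, so categorical ECG counts carry much of the QT description. The one change threshold that survives, 60 msec, is also the level at which protocol 4.3 and 7.9 already require further ECG evaluation. Without the 30 msec row, the change categories say nothing about how many patients had a smaller but still notable rise.

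Because the SAP prevails, a programmer who follows it will not produce the promised count. Because Section 11 is empty, nothing tells the CSR author that there is a difference to explain.

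**Working it through.** No sample size, power or error-rate figure bears on this point. The check sets the two documents side by side and then finds which rises the SAP conditions miss.

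**1. Thresholds compared**

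| Protocol 9.6 | SAP 8.9 |
|---|---|
| above 450 | confirmed, above 450 |
| above 480 | confirmed, above 480 |
| above 500 | confirmed, above 500 |
| change above 60 | increase above 60 (any reading); increase above 60 (confirmed) |
| change above 30 | none |

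Four of the five protocol thresholds survive. The missing one is change above 30 msec.

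**2. Whether another output supplies it.** SAP Table 9 covers heart rate, PR and QRS only. The shift table classes a tracing as normal or abnormal, not by size of change. By-visit descriptive statistics give a mean and a maximum change, not the number of patients past 30 msec. The above-450 row measures something else: a move from 445 to 452 is counted on a rise of 7.

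**3. Which rises go uncounted.** Patients are excluded if QTcF exceeds 450 "msec on 12-lead ECG at screening or day 1 (whichever comes first) of this study", so baseline b is at most 450. For a confirmed rise r with 30 < r ≤ 60, the above-60 conditions do not apply to the confirmed value, and the above-450 condition fails when b + r ≤ 450, that is, when r ≤ 450 − b.

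| Baseline b (msec) | Confirmed rises meeting no confirmed condition |
|---|---|
| 390 or less | 30 < r ≤ 60 (for example 380 to 440) |
| 395 | 30 < r ≤ 55 |
| 400 | 30 < r ≤ 50 |
| 410 | 30 < r ≤ 40 |
| 420 or more | none |

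**4. The proviso.** The fourth SAP condition, increase above 60, is not limited to confirmed values. Take baseline 380 and readings 445, 440 and 432. The average is 1317/3 = 439, a rise of 59, but 445 alone is a rise of 65 and meets condition four. So the table holds only where no single reading at the visit rises by more than 60. At baselines of 420 or more, the above-450 row works on the average, so a single reading above 450 that averages to 450 or less is not counted there.

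**5. Age bands.** Parent week 16 is 16 × 7 = 112 days after parent entry at the earliest, and the week 53 visit is day 371, which is 370 days after day 1. The total is 112 + 370 = 482 days, or 475 with the 7-day visit window. That exceeds a year, so anyone aged 18 at parent entry who reaches week 53 is at least 19 by then. Whether this matters depends on an age reference that the SAP does not state:

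- Age at day 1 or at visit: patients aged 19 or over have no supine blood pressure or pulse criterion.
- Age at parent entry: no gap, since entry was limited to 6-18.

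The documents do not settle it. For direct roll-overs, demographics fall under "Data carried over from Study TV50717-CNS-30080 - Screening" (protocol Appendix C), but on the 2 to 4 week routes they are recorded afresh. SAP 5.3 uses a closed "age group (6 to 11 years, 12 to 18 years" split, which fits parent-entry age. Table 9 is open-ended from 16 years.

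**The case against.** The strongest reply is that little is lost. QTcF is still collected, by-visit changes and worst-case normal/abnormal shifts are still tabulated, and both protocol 9.10 and the SAP Introduction allow a difference to be explained in the CSR. This stands as a limit on severity. It does not restore the count, and it does not make Section 11 correct, since protocol Section 9 expects changes to be described in the SAP itself.

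A reader might infer that with a baseline of 390 or less every rise between 30 and 60 msec escapes all five conditions. The documents do not support that, because condition four can be met by a single reading even when the average is below the threshold.

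A reader might also infer that 19- and 20-year-olds are certainly left without vital-sign criteria, or try to estimate how many there are. Neither is supported. Under parent-entry age nobody is affected, the orthostatic and temperature rows carry no age limit, and the documents give no age distribution from which to project a number.

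On laboratory values, it is fair to say that normal-range shift counts remain for all tests as applicable, and that the protocol does not require the predefined criteria to sit in the SAP. That makes the item an incomplete specification, not a dropped analysis.

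**Conclusion.** The QTcF point holds. Following the SAP as written loses a patient count that the protocol promises twice for the primary objective, no other output replaces it, and Section 11 wrongly reports no change. Its size is one missing category out of five. The number of patients it would contain cannot be known from the documents. The range of uncounted rises in the working rests only on document thresholds and on the proviso about single readings.

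The age and laboratory items are minor clarifications and do not carry the point. The first is an unstated age reference whose effect may be nil. The second is a set of criteria still to be specified. Nothing here suggests that data are lost or that patient management is affected.

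**What to change.** **Main change, SAP 8.9.** Add a row, overall and by visit, for the number and percentage of patients with a QTcF increase from baseline above 30 msec. Show it for any on-treatment QTcF and for confirmed QTcF, as is already done for 60 msec. Keep it outside the QTc prolongation definition, because any condition on that list classifies a value as prolonged and a rise above 30 would enlarge that total.

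**SAP Section 11.** List whatever differences from protocol 9.6 remain. One is that the absolute thresholds apply to confirmed QTcF, where the protocol refers to on-treatment values.

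**Minor clarifications.** For Table 8, state which age is used (parent entry, day 1 or visit), or make the top supine bands open-ended as in Table 9. For SAP 8.5, set PCS laboratory criteria before database lock or declare the omission. The thresholds are for the sponsor to choose.

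**Cost.** One table row in two versions, one age statement or two band labels, and one laboratory table or a one-line declaration. All use data already collected, and study conduct does not change.

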## 7.9.      **Electrocardiography**

A 12-lead ECG will be recorded at the time points detailed in [Table 4](#) and [Table 5](#). All ECGs will be performed after at least 5-minute rest in a supine or semi-supine position. The investigator should review the ECG at day 1 and at screening (in case a screening visit is performed) to determine patient eligibility for the study and subsequent ECGs for the patient's continuation in the study. A qualified physician at a central diagnostic center will be interpreting the ECG.

The ECG types are defined as follows:

- A “standard ECG” is a “standard” 10-second 12-lead ECG.
- A “summary ECG” is a continuously recorded ECG of longer than 10 seconds. For a “summary ECG,” the minimal recommended duration is 2 minutes or longer, and the preferred duration is 5 minutes (as it provides the most robust result). If a “summary ECG” is less than 2 minutes, data will still be captured and analyzed to the extent possible.

The investigator should review the ECG at screening to determine patient eligibility for the study and subsequent ECGs for the patient's continuation in the study. All ECGs should be reviewed by the investigator for any clinically significant findings during the visit, and before the patient leaves the clinic. A qualified physician at Spaulding (the central diagnostic center) will interpret the ECG.

All ECG results outside of the reference ranges will be judged by the investigator as belonging to one of the following categories:

- abnormal and not clinically significant
- abnormal and clinically significant

Any ECG finding that is judged by the investigator as clinically significant will be considered an adverse event, recorded on the source documentation and in the CRF, and monitored as described in [Section 7.1.2](#).

The criteria for an abnormal post-baseline QTcF are a value  $>500$  msec or change from screening  $>60$  msec. If one of these criteria is met, the investigator must further evaluate the QTcF as follows:

- If a standard ECG is abnormal and meets the above protocol criteria:
  - A 5-minute summary ECG recording should be performed at the research site, and a repeat standard ECG is not required. The site should follow the process to have these ECGs read by Spaulding.

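### SAP 8.9 counts QTcF above 450, 480 and 500 msec only on a confirmed value, without the protocol's unqualified on-treatment count; the loss falls mainly on the >500 msec row, and SAP Section 11 does not declare the change

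*SAP*

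**What the plan says.** **Protocol 9.6** (and the synopsis, Analysis of Safety) will present "the number and percentage of patients with on-treatment QTcF values >450, >480, or >500 msec", together with changes from day 1 above 30 and above 60 msec. It attaches no confirmation or averaging condition and is silent on replicate ECGs.

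**SAP 8.9** introduces its list with "QTcF values will be classified as having QTc prolongation if any of the following conditions are met". Each of the three absolute limits is on a confirmed value, for example "Confirmed QTcF >500 msec". For an increase above 60 msec it keeps two rows, one raw and one confirmed. There is no row for an increase above 30 msec. The definition is "The confirmed QTcF is defined as the average of up to 3 standard ECG values at a visit, or a single summary ECG", and then: "If there are more than 3 standard or more than one summary ECG at a visit, then use the last ECGs for the confirmed QTcF". Results are summarised overall and by visit.

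**Protocol 7.9** sets the trigger for further ECGs at a post-baseline QTcF above 500 msec or a change above 60 msec: "If one of these criteria is met, the investigator must further evaluate the QTcF as follows". The first route is "A 5-minute summary ECG recording should be performed at the research site, and a repeat standard ECG is not required". If that cannot be done, two repeat standard ECGs are averaged with the first. SAP 8.9 repeats the trigger and points to that section.

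**SAP Section 11**, on changes from the protocol's analyses, says that none applies. The SAP introduction says that the SAP prevails where the two differ and that the CSR will explain the differences.

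**The concern.** ECG parameters are among the endpoints of the primary, safety objective. A count of patients above 500 msec is one of the first figures a safety reader looks for. The protocol describes a count of values on treatment. The SAP counts something narrower, and the narrowing is selective: extra ECGs are called for only where the reading, or its rise, is large. The highest readings are therefore the ones averaged or replaced before they reach the table, while a moderately high reading is taken as it stands.

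Because the SAP prevails and declares no change, the reported >500 row can be lower than the protocol's wording would give, with nothing in the SAP to tell the reader why. The overall row has a separate mismatch in the other direction, because it is not restricted to ECGs taken on treatment.

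**Working it through.** The plan gives no figure to reproduce here. The check sets the rules side by side and then applies the SAP definition.

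**1. Rows promised and rows planned**

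| Quantity | Protocol 9.6 | SAP 8.9 |
|---|---|---|
| QTcF >450, >480, >500 | values on treatment, no qualifier | confirmed only |
| Change >60 | yes | raw and confirmed |
| Change >30 | yes | absent |
| Period | on treatment | overall and by visit, no restriction |

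**2. Which readings are affected.** A lone standard ECG is an average of one. A reading of 485 msec with no rise above 60 msec triggers nothing, has a confirmed value of 485/1 = 485, and counts as >450 and >480. Readings from 451 to 500 without such a rise are therefore unaffected. Readings above 500, and lower ones with a rise above 60, are affected.

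**3. When a trigger leaves the >500 row**
- *Repeat route.* The confirmed value is (first + repeat 1 + repeat 2)/3. Example: (506 + 490 + 488)/3 = 1484/3 = 494.7, so not >500, but still >450 and >480. In general a first reading F drops out when the mean of its two repeats is at most (1500 − F)/2: 499.5 for F = 501, 497.5 for 505, 495 for 510, 490 for 520 and 480 for 540.
- *Summary route.* If the summary ECG is the value used, the trigger drops out whenever that ECG is 500 or less, whatever the first reading was. SAP 8.9 does not say which value takes precedence when a visit has both a standard and a summary ECG.
- *More than three standard ECGs.* The last ones are used, so the trigger no longer enters the average.

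**4. Where the trigger still shows.** Patients with QTcF above 450 msec at screening or day 1 are excluded (protocol 4.2), so baseline should be at most 450. A reading F misses the raw >60 row only if baseline is at least F − 60. For F = 506 that means 446 to 450. For F = 510 it means exactly 450. For F = 511 it would need 451, which the entry limit rules out. Hence only readings of 501 to 510, with baseline between 441 and 450, can miss that row. No planned row would show the reading as >500.

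**5. Size at the planned enrolment.** With about 45 patients (protocol 9.1), one affected patient moves the row from 0/45 = 0% (exact 95% CI 0 to 7.9%) to 1/45 = 2.2% (0.1 to 11.8%).

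**6. Illustration under assumed values.** Neither the true QTcF nor the within-visit SD is in the documents. Three independent normal readings were simulated with SD 6 to 15 msec. The share of first readings above 500 whose three-ECG mean is at most 500 is:

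| Assumed true QTcF (msec) | Share falling to 500 or below |
|---|---|
| 480 | 93 to 100% |
| 490 | 69 to 98% |
| 495 | 50 to 77% |
| 500 | about 30% |

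**7. Week 54.** Protocol Table 5 schedules an ECG at Week 54. Dosing stops at the Week 53 visit, so this ECG is about a week off drug. The SAP's overall summary does not exclude it. That can only add patients, but they are not in the protocol's on-treatment count.

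**The case against.** The strongest defence is that confirmation is sound practice and matches what the protocol acts on. The stopping rule in protocol 4.3 and 7.9 is itself written on a confirmed average or summary ECG. Protocol 9.6 speaks of values and never says single readings, so the SAP can be seen as supplying missing detail, which its introduction allows. This stands as a reason to keep the confirmed rows. It does not explain why the unqualified count is absent for the absolute limits when SAP 8.9 reports both forms for the >60 msec increase, or why Section 11 is empty.

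The simulation also cuts both ways. With a true value below 500, every reading above 500 is measurement noise, so averaging removes false positives. That is fair. The simulation does not estimate how many patients in this trial would be affected.

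A reader might go further than the documents allow in four ways.
- *All three limits are understated.* Most readings of 451 to 500 count as read.
- *An extreme reading disappears from the report.* It usually enters the raw >60 row, and may show in a by-visit maximum or in the normal/abnormal shift table. What is lost is its count as >500.
- *All conditions collapse into one prolongation flag.* The introductory sentence can be read so, but separate bullets for 480 and 500 would then be redundant.
- *Classification depends on whether the repeat falls at a later visit.* Protocol 7.9 has the ECG reviewed before the patient leaves and schedules no repeat at another visit. In that case the trigger would in any event be counted.

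The rule for more than three ECGs likewise needs recordings beyond the stated procedure, whose fallback route gives exactly three including the trigger.

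**Conclusion.** The point holds in limited form. SAP 8.9 narrows the protocol 9.6 count for the three absolute limits, omits the >30 msec change row, does not restrict the overall summary to treatment, and Section 11 declares none of this. The practical loss falls mainly on the >500 row, plus lower readings that rose by more than 60 msec. At the planned enrolment each affected patient is worth 1/45 = 2.2 percentage points.

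The text conflict rests on no assumption. The limit on which readings miss the raw >60 row assumes that the entry limit of 450 msec was observed. The simulated shares rest wholly on assumed means and SDs and are illustrative. Because the stopping rule uses the confirmed value, the documents do not support inferring that patient management is affected. This is a reporting gap in a primary-safety table that should be closed before database lock.

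**What to change.** In SAP 8.9:
1. For each of 450, 480 and 500 msec, give two separate rows: (a) patients by maximum single on-treatment QTcF, always keeping the triggering ECG, and (b) patients by confirmed value.
2. State which value is the confirmed one when a visit has both standard and summary ECGs.
3. Limit the overall rows to ECGs on treatment and show Week 54 separately.
4. Restore the row for change above 30 msec.

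In SAP Section 11, list any difference from protocol 9.6 that remains.

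The cost is SAP wording and a few table rows. No new data are needed, and the stopping rule is untouched. The raw rows may look slightly less favourable and will include some readings that repeats did not bear out, which is why the confirmed rows should stand beside them.
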